## 1. The BUMPES Randomised Controlled Trial

Full details of the primary and secondary objectives of the BUMPES study, trial design, eligibility, and so on can be obtained from the main study protocol and the statistical analysis plan study that are available in separate documents. Briefly, BUMPES is a pragmatic multicentre randomised controlled trial (RCT) assessing the effectiveness of: 1) an upright maternal position (intervention group) which would maintain the pelvis in a vertical plane as possible; and 2) a lying down maternal position (control group) which would maintain the pelvis in a horizontal plane as possible. Both interventions begin during the second stage of labour with the intention of continuing the allocated position up until the birth. The BUMPES study will evaluate postnatal maternal and neonatal morbidity and well-being assessed one year after birth.

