**Table 1: Summary of the BUMPES economic evaluation**

Summary	Description
Health Outcome	Maternal Quality Adjusted Life Years (QALYs)
Cost	Delivery procedure costs, original hospital admissions, readmissions, health care visits (for mother and babies)
Timeframe	1 year (12 months) follow-up after birth
Data	Approx. 1,500 women (750 women in each arm)
Data collection	Data collection booklet and maternal questionnaire at one year after birth
Analysis	Intention to treat analysis
Cost-effectiveness results	Cost per QALY gained

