A descriptive analysis will provide information about how serious is the presence of missing data in resource use, costs and utilities at one-year follow-up. The decision to impute or not missing data and what exactly to impute will be based on current guidance. If imputation techniques need to be implemented, we will use multiple imputation with chained equation methods and will attempt to impute all components in the economic evaluation. However, this may not be possible due to the

amount of missing data and type of model used and at minimum costs and QALYs will be included in the imputation model. We will combine the statistics of interest (e.g. means and standard errors in each group) using appropriate Rubin rules.

Uncertainty around the cost per QALY gained will be expressed calculating 95% confidence interval around the incremental cost-effectiveness ratio (if appropriate) and using cost-effectiveness acceptability curves (CEACs). We will also present the results of the cost-effectiveness analysis using the net benefit statistics. A full parametric approach will be used to derive ICER's confidence intervals and CEACs. We may implement a bootstrap method to estimate pairs of mean costs and QALYs for each intervention to present uncertainty around cost-effectiveness results using the cost-effectiveness plane.

We will discuss with the clinical team whether cost-effectiveness is likely to vary for a particular subgroup(s) of women and will derive cost-effectiveness results for such subgroups. The subgroup analysis will follow the same methods as the primary analysis.

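### Each economic subgroup gets its own stand-alone result, no comparison between subgroups is planned and the subgroups are not fixed in advance, so differing subgroup results cannot be told from chance

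*Combined protocol and SAP*

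**What the plan says.** The closing paragraph of section 3.6 (Analytical methods) is all that the document says on economic subgroups. Selection: "We will discuss with the clinical team whether cost-effectiveness is likely to vary for a particular subgroup(s) of women". Output: the team "will derive cost-effectiveness results for such subgroups". Method: "The subgroup analysis will follow the same methods as the primary analysis".

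The methods carried over are set out earlier in section 3.6:

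- mean differences in costs and utilities between arms by parametric methods;
- an ICER with a 95% confidence interval where appropriate;
- acceptability curves;
- net benefit ("We will also present the results of the cost-effectiveness analysis using the net benefit statistics");
- possibly a bootstrap for the cost-effectiveness plane.

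The paragraph names no subgroup. It gives no number of subgroups, no date by which they are chosen, no interaction analysis, no rule for multiplicity and no exploratory label. No willingness-to-pay value appears anywhere in the supplied text.

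Section 1 says that full details of objectives and design "can be obtained from the main study protocol and the statistical analysis plan study that are available in separate documents". Section 3.6 refers to the main statistical analysis plan for the intention-to-treat principle, but not for subgroups.

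**The concern.** Whether cost-effectiveness varies between groups of women is a question about the difference between subgroup results. Repeating the arm comparison inside each subgroup gives two or more separate answers and no measure of how far apart they are relative to noise. Each answer also rests on fewer women than the overall result, so the separate estimates scatter more widely.

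What is at stake is how the subgroup results will be read. Suppose one subgroup's acceptability curve lies above 50% at a given threshold and another's lies below. A reader may conclude that the better-value position differs between these women. Under the planned parametric normal approach, a curve crosses 50% where estimated net benefit changes sign, so such a picture can arise from sampling error alone. Because the subgroups are open and the timing of their choice is not stated, a reader also cannot tell whether the ones shown were settled before results by arm were known.

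**Working it through.** **Inputs from the document.** Table 1 gives about 1,500 women, 750 per arm (2 × 750 = 1,500). It gives no SD, expected net benefit, subgroup size or subgroup error rate, so the plan has no figure of its own to reproduce on this point.

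**Assumptions.** Estimated incremental net benefit is normally distributed. True net benefit is identical in all women and equals z standard errors (SE) of the overall estimate. Subgroups are equal halves. The values of z are illustrative.

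**One factor, two equal halves.** Each half has an SE √2 times the overall SE, so the chance that its estimate is positive is p = Φ(z/√2). The chance that the two halves have opposite signs is 2p(1 − p).

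- z = 0: p = 0.500; 2 × 0.500 × 0.500 = 50%
- z = 1: p = 0.760; 2 × 0.760 × 0.240 = 36%
- z = 2: p = 0.921; 2 × 0.921 × 0.079 = 14%
- z = 2.8 (overall effect with 80% power): p = 0.976; 2 × 0.976 × 0.024 = about 5%
- z = 3.24 (90% power): p = 0.989; 2 × 0.989 × 0.011 = about 2%

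**Three balanced, mutually independent factors.** Every factor splits the same women, so all three splits share one overall estimate. In units of the overall SE, write that estimate as X ~ N(z, 1). Factor k gives half-sample estimates X + D_k and X − D_k, with D_k ~ N(0, 1). Its halves disagree in sign when |D_k| > |X|. The chance that at least one of the three disagrees is therefore 1 − E[(2Φ(|X|) − 1)³], which gives:

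- z = 0: 75%
- z = 1: 59%
- z = 2: 28%
- z = 2.8: 10%

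The shortcut 1 − (1 − q)³, with q the one-factor probability, treats the three disagreements as independent. It overstates the risk (74% instead of 59% at z = 1).

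**On a money scale, with assumed SDs of net benefit and complete data.** For SDs of £3,000, £5,000 and £8,000, the overall SE is SD × √(2/750) = £155, £258 and £413. The half-sample SE is SD × √(2/375) = £219, £365 and £584. For a true net benefit of £300 in every woman, the halves disagree in sign 16%, 33% and 42% of the time.

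**What an interaction analysis could show.** With equal halves, the SE of the difference between subgroups is √(2 + 2) = 2.0 times the overall SE. For a 75/25 split it is √(1/0.75 + 1/0.25) = 2.31 times. For an interaction as large as an overall effect that has 80% power (2.8 SE), two-sided 5% power with equal halves is Φ(2.8/2 − 1.96) = Φ(−0.56) = about 29%.

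**The case against.** Five points can be made for the plan.

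1. **No decision rule.** A reader might infer that chance will often produce opposite recommendations for different women. The documents do not support this. The plan never says that a recommendation follows the sign of net benefit. It carries confidence intervals and acceptability curves into each subgroup, where a noisy result would look noisy. At zero effect, two halves that are each significant in opposite directions would occur only 2 × 0.025 × 0.025 = 0.125% of the time. This stands against the strong reading. It does not close the gap, because displays of uncertainty within each subgroup do not state the uncertainty of the difference between them.

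2. **Frequency unknown.** With a clear overall effect, a single equal split rarely disagrees in sign (2–5% at 3.24–2.8 SE). The number of factors is also unknown; the plan speaks of one or more subgroups. This stands, and the figures above are illustrations only.

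3. **Choice by clinical judgement.** The wording makes likely variation the criterion for picking subgroups and does not announce a hypothesis test. This is fair and is better than searching the results. Still, nothing says that the choice comes before results by arm are seen, and once results are shown by subgroup the reader will ask whether they differ.

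4. **Unseen documents.** The main statistical analysis plan may list subgroups. That cannot be checked here, and the economic section does not tie its own subgroups to any such list. Absence of an interaction analysis is an omission in this text and not an explicit exclusion.

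5. **Secondary analysis.** The overall cost-effectiveness result is untouched. This limits the seriousness of the point.

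**Conclusion.** The point holds in a limited form. Section 3.6 prescribes a method for subgroups that compares arms only, so it cannot show whether cost-effectiveness differs between subgroups, and the subgroups are not fixed in advance. The missing between-subgroup comparison is the substantive fault; the lack of named subgroups taken alone would be a missing detail.

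How often chance would mislead cannot be fixed from the documents. If net benefit is truly the same in everyone, sign disagreement in one equal split runs from 50% when the overall net benefit is zero to about 5% when it is 2.8 SE. For three balanced independent factors the range is 75% to 10%. These figures rest on normality, equal halves and assumed values of z. They describe point estimates, not the recommendations that the authors would make. The change should be made, but it bears on a secondary analysis and not on the main result.

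**What to change.** Replace the last sentence of section 3.6 with a rule to this effect: for each subgroup factor, a net-benefit regression is fitted to all women with terms for arm, subgroup and arm by subgroup, at willingness-to-pay values stated in the plan, and the interaction estimate is reported with its 95% CI. Those values have to be added, since none is given at present.

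Also state:

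- which subgroups will be examined and why, fixed before results by arm are seen (using those in the main statistical analysis plan if it lists any);
- how many factors are examined;
- that subgroup acceptability curves are exploratory and are shown beside the overall curve.

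The cost is some wording and one regression per factor at each stated willingness-to-pay value; net benefit is already planned. There are two downsides. Power for the interaction is low (about 29% in the case worked above), so a non-significant interaction must not be read as evidence that cost-effectiveness is the same in all women; the estimate and its interval matter more than the p-value. And subgroups that were not planned could no longer be headlined.
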